## **Specific objectives**

1. To assess the effect of daily dietary supplementation with Biobran/MGN-3 (500 mg/d for 3 months) on the incidence rate of influenza-like illnesses in older adults. The incidence rate will be calculated by dividing the number of incident ILI cases by the total number of the group participants.
2. To assess the effect of daily dietary supplementation with Biobran/MGN-3 (500 mg/d for 3 months) on the incidence density of influenza-like illnesses in older adults. The incidence density will be calculated by dividing the number of incident cases by the total person-time at risk.
3. To assess the effect of daily dietary supplementation with Biobran/MGN-3 (500 mg/d for 3 months) on NK number and activity in geriatric population. Activity of NK cells will be assessed using the degranulation assay.
4. To assess the effect of Biobran/MGN-3 (100 µg/ml for 72 h) on the pulmonary epithelial BEAS-2B cell lines expression levels of viral nucleic acid sensors Retinoic Acid-Inducible Gene 1 (RIG-1) and Melanoma Differentiation-Associated protein 5 (MDA5) as well as some of their downstream antiviral proteins Interferon-stimulated Genes 15 (ISG15), and Myxoma Resistance Gene 1 (MX1) using flow cytometry.

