### 3. Subjects:

Ninety apparently healthy older adults  $\geq 56$  years were originally recruited from the residents of Zagazig city visiting outpatient clinics at Zagazig University Hospitals. Only local residents were recruited so as to facilitate follow-up home visits and to reduce the dropout rate. Old age is associated with NK cell senescence. We recruited subjects  $\geq 56$  years of age in order to meet the WHO definition of old age in African nations (32). In addition, this age is close to public service retirement in Egyptian society, which is associated with significant social, mental, and psychological stress and therefore could be associated with significant decline in NK activity.

Males and females were randomly assigned into two groups (n=40/group) that received either placebo or Biobran/MGN-3 (500 mg/day for 3 months). Both the health care giver and the participants were blinded to the ingested supplement. Participants' health were monitored via weekly home visits and they were instructed to report any complaint or side effect by phone to the health care giver.

Diagnosis of ILI was made by documenting the incidence of acute respiratory illness with a measured temperature of  $\geq 38$  °C with cough (Fitzner et al., 2017). After diagnosis, the subject was helped to follow the proper health management

plan by the health care giver. During the study, all participants were required not to take any vitamins or medications during the study without consultation.

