**Sample size:**

Previous clinical trials demonstrated that daily intake of Biobran/MGN-3 in young adults at doses of 15 mg/kg/d (~1000 mg/d), which is around 2 folds of the dose (500 mg/d) used in the current study, and 30 mg/kg/d (~2000 mg/d) increased NK cells activity after one month by 2 folds and 5 folds, respectively (Ghoneum,

1998). Therefore, it is reasonable to propose that doses of 500, 1000, and 2000 mg/d are within the linear portion of the Biobran/MGN-3 dose response curve. Thus, it is expected that Biobran/MGN-3 at a dose of 500 mg/kg will yield an effect size of 0.8. A power analysis using this effect size for a repeated measure analysis of variance with two measurements was performed using G\*Power software package (version 3.1.9.2, Franz Faul, Germany). With the criterion of significance (alpha) set at 0.05, a sample size of 13 subjects per group (total of 39 subjects) results in a power of 0.80 to yield a statistically significant result regarding NK cell activity.

With regards to the preventive efficacy on influenza-like illnesses, we propose to enroll 90 subjects as a pilot study.

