### **2. Laboratory investigation:**

**Blood sampling, plasma and PBMCs isolation:** Study participants will be asked to donate blood samples (10 ml) at the start (basal) and at the termination of the study (4 weeks). Blood will be collected into heparinized tubes, diluted with an equal volume of DPBS (no  $\text{Ca}^{++}/\text{Mg}^{++}$ ), and peripheral mononuclear cells (PMBC) will be isolated by a standard Ficoll-Hypaque density gradient centrifugation method within 2h. Part of the plasma will be aspirated and frozen for analysis of liver and kidney functions. The lymphocyte band will be aspirated from the gradient interface, washed once with PBS supplanted with 1 mM EDTA and 0.1% BSA to remove platelets and once with a complete medium (CM; RPMI medium supplemented with 10% fetal bovine serum, 100-U/ml penicillin, 100 mg/ml streptomycin and 50 mg/ml gentamicin.), counted and assessed for viability in a trypan blue dye (0.2% (v/v) in PBS), and prepared as subsequently described for the different assays.

**Liver and kidney functions:** AST (serum glutamic oxaloacetic transaminase or SGOT), ALT (serum glutamic-pyruvic transaminase or SGPT), uric acid, creatinine will be assessed in plasma.

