### **3. Statistical analysis:**

Fisher's Exact test and OpenEpi, version 3.01, was used for comparing the incidence rates and the incidence density rates between groups. Mean  $\pm$  standard deviation is used to express continuous variables. Shapiro-Wilks test was used to determine the normality of data distribution. Two-tailed Student's t-test was used to compare Biobran/MGN-3 and placebo groups. Paired t-test was used to examine treatment effects within groups (i.e., comparisons of post-treatment versus pre-treatment).  $P \leq 0.05$  was considered statistically significant. SPSS version 20 was used for computing statistical analyses values.

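### The NK analysis leaves the between-arm variable open, makes no stated use of the baseline value, and calls within-arm paired tests treatment effects

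*Combined protocol and SAP*

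**What the plan says.** The Statistical analysis section gives two tests for continuous variables. The between-arm test is "Two-tailed Student's t-test was used to compare Biobran/MGN-3 and placebo groups". The within-arm test is described as follows: "Paired t-test was used to examine treatment effects within groups (i.e., comparisons of post-treatment versus pre-treatment"). One significance threshold, P ≤ 0.05, covers both. The section does not mention NK activity, sets no order between the tests, and does not name the variable for the between-arm test.

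Other sections bear on the point but do not settle it:

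- **Specific objectives.** The third objective is to assess the effect of supplementation ("500 mg/d for 3 months) on NK number and activity in geriatric population"). It names no between-arm contrast. The NK research question names no comparator either.
- **Sample size.** NK activity is sized on a "repeated measure analysis of variance with two measurements". The section does not say which effect of that model is meant. The stated result is that "a sample size of 13 subjects per group (total of 39 subjects) results in a power of 0.80". The section ties this power to NK activity and to no other outcome.
- **Subjects.** "Males and females were randomly assigned into two groups (n=40/group").
- **Laboratory investigation.** Blood is taken "at the start (basal) and at the termination of the study (4 weeks"), so every participant who gives both samples has a baseline NK value.

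**The concern.** The trial has a blinded placebo arm so that changes unrelated to the supplement can be subtracted out. A paired test in one arm ignores that control. If NK activity drifts over the winter months, with the assay, or through placebo response, the paired test in the active arm will detect the drift. Calling the result a treatment effect invites the reader to compare two P values, one per arm, instead of testing the difference between arms.

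The between-arm test is the valid comparison, but its variable is not fixed. Final value and change are both defensible, and they can give different answers on the same data. If the choice waits until the data are seen, the nominal 5% no longer holds. Neither option as listed makes stated use of the baseline value as a covariate, although that value is already collected.

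**Working it through.** **Inputs from the documents.** Two arms with 40 per group (Subjects); two NK measurements (Laboratory investigation); P ≤ 0.05 and a two-tailed between-arm test (Statistical analysis); effect size 0.8 and 13 per group, total 39, for power 0.80 (Sample size).

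**Assumed, because the documents give no figure.** A shift common to both arms, in SD of the change score (dz); the baseline–final correlation r, taken as 0.3, 0.5 and 0.7; normal data; and 0.8 read as a standardised between-arm difference in final values.

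**1. The plan's own figure.** The sample-size statement is not reproduced as a whole: 2 × 13 = 26, while 39 = 3 × 13. Thirteen per group alone can be approached only with undeclared choices. For example, a paired comparison with dz = 0.8 under the normal approximation gives 13, but the exact paired t gives 15, with 75% power at 13. A two-group repeated-measures ANOVA with f = 0.4 gives 14 per group at correlation 0. Its interaction gives 13 at correlation 0.1 and 8 at 0.5. A two-sample t-test on final values at d = 0.8 needs 26 per arm. The stated figure therefore does not reveal which comparison was meant.

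**2. Reading the two paired tests against each other, no true effect.** Let p be the two-sided power of the paired t-test (noncentral t, n − 1 df, noncentrality dz√n). The arms are independent, so P(active significant, placebo not) = p(1 − p), which cannot exceed 0.25. With n = 40:

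| Common shift dz | p | p(1 − p) |
|---|---|---|
| 0 | 0.050 | 0.048 |
| 0.1 | 0.095 | 0.086 |
| 0.2 | 0.235 | 0.180 |
| 0.3 | 0.457 | 0.248 |
| 0.4 | 0.694 | 0.212 |
| 0.5 | 0.869 | 0.114 |
| 0.6 | 0.959 | 0.039 |
| 0.8 | 0.999 | 0.001 |

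The rate rises to a peak near dz = 0.31 and then falls, because large shifts are significant in both arms.

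**3. Leaving final value or change open, no true effect.** With equal baseline and final variances, the two between-arm differences correlate at √((1 − r)/2), that is 0.59, 0.50 and 0.39 for r = 0.3, 0.5 and 0.7. They are far from interchangeable. In a null simulation (bivariate normal, 100,000 runs per cell, 40 per arm), final value, change and ANCOVA each reject in 4.9% to 5.1% of trials when used alone. Rejecting if either final value or change is significant gives 8.8%, 9.1% and 9.4%. Counting only results that favour the supplement, the rate is about 4.2% to 4.7%, against 2.5% for one fixed test. A common shift cancels between arms, so these rates hold at any shift.

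**4. Power at d = 0.8, 40 per arm.** Final value: two-sample t with noncentrality 0.8 × √(40/2) = 3.58. Change: the standardised difference becomes 0.8/√(2(1 − r)) = 0.68, 0.80 and 1.03. ANCOVA: simulated.

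| r | Final value | Change | ANCOVA |
|---|---|---|---|
| 0.3 | 94.2% | 84.8% | 95.8% |
| 0.5 | 94.2% | 94.2% | 98.2% |
| 0.7 | 94.2% | 99.5% | 99.8% |

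The gain of ANCOVA over final values is 95.8 − 94.2 = 1.6 points at r = 0.3 and 99.8 − 94.2 = 5.6 points at r = 0.7, or about 2 to 6 points.

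**The case against.** The strongest reply is that the plan already contains the right comparison. The between-arm t-test comes first, the design is double-blind and placebo-controlled, and the paired test is defined in its own sentence as post versus pre. The natural reading is then a between-arm test plus within-arm description, with one loosely worded phrase. Much of this stands. A reader might infer that efficacy will be judged on the active arm's paired test, but no section says so. The 46% rejection rate of that test alone at a 0.3 SD shift therefore describes something the plan does not propose.

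The 25% is also a peak at one assumed shift, not an expected rate, and the 9% counts errors in both directions and assumes that the better result is picked. Both qualifications are right and are built into the figures given here.

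A reader might also infer that the sample-size model contradicts the analysis section. That is not established. With two groups and two measurements, the group-by-time interaction of a repeated-measures ANOVA is the same test as a t-test on change, so the gap may be only apparent. The text does not say which effect was meant.

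Nor do the documents support a claim that the NK comparison is underpowered at 13 per group: no section limits NK assays to such a subset, and blood is requested from study participants generally.

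Finally, ANCOVA is not the only valid choice, and its power gain here is small. That is correct. Two things remain: the role and variable of the between-arm test are unstated, and a within-arm test carries the label of a treatment effect. Calling the study a pilot does not answer this, because the Sample size section uses that word for influenza-like illness, whereas NK activity was sized for 80% power.

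**Conclusion.** The point holds as a gap in specification and a misleading label, not as evidence that the trial will draw its NK conclusion from the wrong test. The plan does include a between-arm comparison. It does not say that this comparison decides the NK objective, does not fix its variable, and makes no stated use of the baseline as a covariate.

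If the variable is chosen after the data are seen, the two-sided error rate is about 9% instead of 5%, for r between 0.3 and 0.7. If a reader compares the two paired P values under an equal shift and no true effect, the misleading pattern occurs in anything from about 5% (no shift) to 25% (near 0.3 SD) of trials, then 11% at 0.5 SD and 0.1% at 0.8 SD. These are scenarios: the documents give neither the shift nor the correlation.

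The correction is worth making because it is cheap and protects the one NK comparison that randomisation supports. The timing of the final NK sample (4 weeks under Laboratory investigation, 3 months of supplementation under Specific objectives) is a separate inconsistency and adds no weight to this point.

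**What to change.** In the Statistical analysis section:

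1. State that NK activity is compared between arms by ANCOVA, with the final value as outcome and arm and baseline value as terms. Report the adjusted mean difference with its 95% CI, and state that this comparison decides the NK activity objective. NK activity comes first because the sample size is built on it.
2. State that NK number is analysed the same way as a secondary measure and does not alter that decision.
3. Reword the paired comparisons as changes within groups, reported descriptively (mean and SD) with no efficacy conclusion.

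A between-arm t-test on change, named in advance, is a valid minimum alternative. The essential step is to fix one between-arm test and its variable.

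In the Sample size section, state which effect of the repeated-measures ANOVA was meant, so that it can be matched to the chosen analysis. Separately, the Specific objectives and Laboratory investigation sections must be reconciled on when the final NK sample is taken.

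The cost is a few lines of text, one degree of freedom, and the assumption of a roughly linear baseline slope common to both arms. No new samples are needed, and the model runs in the SPSS version already named.

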## **Research questions**

1. Could Biobran/MGN-3 supplementation reduce the incidence of influenza-like illnesses in older adults?

2. Could Biobran/MGN-3 supplementation reduce the incidence density of influenza-like illnesses in older adults?
3. Does Biobran/MGN-3 supplementation increase NK cell activity in the geriatric population?
4. Does Biobran/MGN-3 supplementation upregulate expression of RIG-1, MDA5, ISG15, MX1?

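### No primary endpoint is named and every comparison is judged at an unadjusted 0.05, so a chance finding among four participant outcomes can be declared significant in roughly 12–14% of null trials

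*Combined protocol and SAP*

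**What the plan says.** The Statistical analysis section of the combined protocol and SAP lists these tests:

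- For ILI, Fisher's exact test and OpenEpi software, which "was used for comparing the incidence rates and the incidence density rates between groups".
- For continuous outcomes, "Two-tailed Student's t-test was used to compare Biobran/MGN-3 and placebo groups".
- Within groups, "Paired t-test was used to examine treatment effects within groups".

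A single threshold covers them all: P of 0.05 or less "was considered statistically significant". The section gives no order of testing, no adjustment, and no split between confirmatory and exploratory results.

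The rest of the document does not settle which endpoint leads. The first research question is clinical: "Could Biobran/MGN-3 supplementation reduce the incidence of influenza-like illnesses in older adults". Incidence density is second. The third objective concerns the effect "on NK number and activity in geriatric population". The only power calculation, in Sample size, is for NK cell activity: "With the criterion of significance (alpha) set at 0.05". The same section then says: "With regards to the preventive efficacy on influenza-like illnesses, we propose to enroll 90 subjects as a pilot study". The Hypothesis section nonetheless includes improved resistance to ILI, with no limit on what an ILI P value may support.

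**The concern.** By order of listing, ILI incidence is the lead endpoint. By sample size, NK activity is. The analysis section treats all outcomes alike. Followed as written, the plan lets whichever comparison falls below 0.05 become the trial's result, although the 5% error rate applies to each test and not to the trial.

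The paired tests add to this. The plan describes them as examining treatment effects, yet a before-after change in one group has no placebo comparison behind it.

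For ILI there is a second problem. The plan labels this part a pilot but produces a significance verdict for it, and says nothing about how that verdict should be read at this size.

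**Working it through.** **1. The plan's own sizing figure.** Inputs from Sample size: effect size 0.8, repeated-measures ANOVA with two measurements, alpha 0.05, power 0.80, stated as 13 per group and 39 in total. Assumptions: 0.8 is a standardised difference (f = 0.4), two groups, within-person correlation 0.5. The noncentrality is λ = f² × N × m / (1 + (m − 1)ρ).

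- N = 39: λ = 0.16 × 39 × 2 / 1.5 = 8.32, power 0.802. The total of 39 reproduces.
- 2 × 13 = 26: λ = 0.16 × 26 × 2 / 1.5 = 5.55, power 0.62. The per-group figure does not fit two groups.

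This calculation gives the whole 0.05 to NK activity, with nothing reserved for other endpoints.

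**2. Which tests count.** Four between-group tests on participants: ILI incidence, ILI incidence density, NK number and NK activity. RIG-1, MDA5, ISG15 and MX1 are measured in BEAS-2B cells treated with PBS or Biobran, so they are left out. The liver and kidney tests are also left out.

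**3. Bound for independent tests.** 1 − 0.95⁴ = 1 − 0.8145 = 18.5%.

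**4. Allowing for correlation.** Null simulations assumed a 20% ILI risk and 40 per group for ILI.

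- With NK measures correlated 0.3: either ILI test 4.7%, either NK test 9.8%, any of the four 14.0%. Check: 1 − (0.953 × 0.902) = 14.0%.
- With 13 per group for NK: either ILI test 4.8%, any of the four 14.3%.
- A further simulation gave about 12% for any of the four.
- Counting within-group paired NK tests as treatment effects raises the total to about 20–30%. It was 29.5% in the run with 13 per group for NK and a before-after correlation of 0.5.

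**5. ILI alone.** Fisher's test is conservative: its actual size at 40 per group and 20% risk is 2.8%. The two ILI measures share the same events, and together they stay below 5%. The excess comes from having ILI, two NK measures and the paired tests side by side.

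**6. ILI power.** Exact enumeration of Fisher's test at 40 per group (Subjects section), with risks assumed because the documents give none:

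| Placebo v active risk | Power |
|---|---|
| 10% v 5% | 4% |
| 20% v 10% | 16% |
| 30% v 15% | 28% |
| 20% v 5% | 41% |
| 30% v 10% | 53% |
| 40% v 10% | 85% |

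The Subjects section gives both 90 recruited and 40 per group. At 45 per group, 20% v 10% has 18% power, so the conclusion does not turn on which total is right. For 80% power to detect a halving, about 435, 199 and 121 per group are needed at control risks of 10%, 20% and 30%.

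**7. What an ILI result would look like.** With 8/40 cases on placebo, Fisher's test reaches 0.05 only if the active group has 1/40 or fewer, an observed reduction of at least 1 − 1/8 = 87.5%. An observed 8/40 v 4/40 has a 95% interval (Newcombe) for the risk difference of about −6 to +26 points.

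**The case against.** Several stronger readings are tempting, and the documents do not support them.

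- *A reader might count eight or more tests and quote 30–34%.* That needs the four cell-line proteins. They are not participant outcomes, cannot show efficacy in participants, and have no test named for them in the analysis section.
- *A reader might say that testing ILI twice inflates the error.* Step 5 shows that it does not exceed 5%.
- *A reader might say the plan treats ILI as confirmatory.* It never uses that word, and a P value in a declared pilot is common practice. What stands is narrower: the pilot label in Sample size has no counterpart in the analysis section.
- *A reader might call the ILI comparison uninformative whatever happens.* Power runs from 4% to 85% over the assumed risks, so a very large effect on a common illness could be detected.

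Two further objections carry weight. A small supplement trial need not adjust for multiplicity, and none is demanded here. The choice of primary also belongs to the sponsor: ILI is the first-listed objective, and the NK calculation has its own inconsistency (13 per group against 39 in total) and uses a model that the analysis section does not plan. The fix therefore leaves the ILI option open. None of this supplies a primary endpoint or tells the reader which result the 5% applies to.

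**Conclusion.** The point holds in limited form. With one unadjusted threshold and no primary endpoint, the chance of at least one false positive among the four participant comparisons is about 12–14%, bounded by 18.5% under independence, and about 20–30% if paired tests are read as treatment effects. The simulated figures rest on a 20% ILI risk and on the assumed correlations. The paired-test figure also assumes no change over time in either group; a seasonal or other time trend would raise it.

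For ILI the issue is interpretation and not inflation. A halving of risk would usually be missed (power 4% to 28%), so an estimate with its interval is a better output than a significance verdict. The trial can run as planned, but a claim based on whichever test succeeds would not carry the stated 5% error rate.

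**What to change.** Amend the Statistical analysis section as follows.

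1. Name one primary analysis: the between-group comparison of NK activity (degranulation assay) at 0.05, the only endpoint with a sample-size calculation. If the sponsor prefers ILI, the section must say so and the pilot label must go.
2. State the single time point of that comparison, and whether it uses final values or change. First reconcile Laboratory investigation, which puts the final blood sample at 4 weeks, with Specific objectives, which describe 3 months.
3. Report ILI incidence and incidence density as pilot estimates, with a risk difference and a rate ratio and their 95% confidence intervals, and no efficacy claim from P of 0.05 or less.
4. Label NK number and the cell-line proteins exploratory.
5. Make the within-group paired tests descriptive, not evidence of a treatment effect.
6. Parts of the document describe recruitment and analysis in the past tense. If outcome data have already been seen, label the choice of primary post hoc.

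The number of participants assayed for NK should be stated too. Reading 0.8 as a standardised difference, a two-sided t-test at 0.05 has 94% power with 40 per group but 50% with 13.

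The cost is a few sentences, with no new data or participants. The downside is that a nominally significant ILI or secondary result could be reported only as exploratory, which for ILI matches the plan's own label.
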